4.4. Screening failure

Participants who are not fulfilling inclusion/exclusion criteria at any stage during the screening period (D-28 to D-1) will be defined as screen failures. All screen failures will be documented in source data, on the screening log and in the eCRF. The screening log will be kept in the Investigators Site File.

4.5. Removal / Early Withdrawal

Participants are free to discontinue their participation in the study at any time, without prejudice and with any obligation to give his/her reason(s) and without any change in their treatment related to safety follow-up. The Investigator must withdraw any participant from the study if he/she requests to be withdrawn, or if it is determined that continuing would result in a significant safety risk or may affect the well-being of the participant.

³ https://www.cdc.gov/coronavirus/2019-ncov/need-extra-precautions/people-with-medical-conditions.html?CDC_AA_refVal=https%3A%2F%2Fwww.cdc.gov%2Fcoronavirus%2F2019-ncov%2Fneed-extra-precautions%2Fgroups-at-higher-risk.html

In addition, the participant may withdraw/be withdrawn for any of the following reasons:

- Administrative decision by the investigator / sponsor
- Ineligibility (identified at any time during the study) ‘in the case it is considered to be in the best interest of the subject’s health’
- Significant protocol deviation
- Non-compliance with study procedures/requirements
- Occurrence of an AE, which at the opinion of the investigator requires discontinuation of the participant or results in inability to continue to comply with study procedures/requirements
- Participant (Female) who become pregnant during the study
- Lost to follow-up

The reason for withdrawal, in case provided, will be recorded in the participant’s source data and in the e-CRF. If withdrawal is due to an AE, appropriate follow-up visits or medical care will be arranged, with the agreement of the participants, until the AE has resolved or stabilized.

In case of lost to follow-up, at least 2 contacts attempts must be made within 1 week to contact any participant lost to follow-up prior to the last scheduled visit. All attempted contacts (e.g. phone contact, post mail, email) will be documented in the participant’s source data.

4.6. Handling of Withdrawals

If a participant is withdrawn from the study at his/her request or further to the Investigator’s decision, information and reason of withdraw will be documented in the participant’s source data and recorded in the eCRF.

Upon withdrawal from the study, any time after first vaccination has taken place, the participant will be encouraged to attend an Early Termination visit (ET) (see section 7.2.13). All relevant investigations scheduled should be performed if the participant agrees. If, however, for any reason the participant does not agree to return to the investigational site for the Early Termination visit, this will be documented in the participant’s source data and recorded in the e-CRF.

If a participant is withdrawn from the study at his/her request, his/her coded data and biological materials stored in the study biobank may be erased/destroyed further to his/her request. However, some data and biological materials previously collected may not be erased/destroyed if their deletion/destruction is likely to render impossible or seriously compromise the achievement of the study objectives or to satisfy a legal or regulatory obligation.

4.7. Replacement Rules

Participants who are discontinued before randomization will be regarded as screening failures and screening will be continued until 90 participants will be enrolled and randomized. Screen failed participants may be eligible for re-screening once.

Participants who withdraw or are withdrawn after enrollment and randomization will not be replaced. This may result in a decreased number of participants in the predefined sample size.

4.8. Individual participants halting rules

The following are specific criteria for discontinuing individual participants from further vaccination, but not from completing scheduled follow-up assessments, unless the participant is explicitly withdrawn from the study:

- Participants who experienced a Serious Adverse Reaction (i.e. a Serious Adverse Event considered at least possibly related to vaccine).
- Participants who experienced a severe (grade 3 or higher) non-serious adverse event considered as at least possibly related to the vaccine
- Participants who develop a medical condition for which continued participation, in the opinion of the investigator, would pose a risk to the participant or would be likely to confound interpretation of the results
- Participants with a confirmed SARS CoV-2 infection given by a positive RT-PCR or a positive serology.
- Participants who donate whole blood or blood derivatives, tissue or organ all along the study.
- Participants who become pregnant during the treatment phase of the study.
- Participants not using a reliable method of contraception
- Participants who experience hypersensitivity reaction such as anaphylaxis within 24 hours or generalized urticaria within 72 hours after administration of the study vaccine
- Participants who use immunosuppressive drugs
- Participants who receive immunoglobulin or other blood product before study completion.
- Participants who live and/or work with severely immunocompromised people, pregnant women, lactating women, children under 12 months old, or any other individual that, in the judgment of the investigator, might be at increased risk from the first vaccination (D0) up to 28 days after the second vaccination (D56).

If any of these occur, appropriate measures to treat the participant will be taken and the participant will be asked to perform an ET visit if the participant is withdrawn (for any reason) from the study. The sponsor will be notified immediately.

4.9. Study halting rules, early study termination, end of study

4.9.1. Study halting rules

The study could be temporally suspended, pending a full DSMB safety review. The criteria for considering a contraindication or preventive action to the start of the treatment of cohort B and C (increasing dosage) or administration of the COVID-19 vaccine to subsequent subjects in the current cohort will be:

- A serious adverse reaction (i.e. a serious adverse event considered at least possibly related to the study vaccine) in one subject.
- The occurrence of clinically significant severe (grade 3 or higher) non-serious adverse events considered as at least possibly related to the vaccine administration in two subjects in the same cohort, independent of within or not within the same system-organ-class. Both clinical and laboratory abnormalities are considered.

- Any onset of AESI assessed as related to the vaccine by the investigator or by the sponsor.

After complete safety review by the DSMB and taking into account its recommendation, sponsor will decide if the study (i.e. new inclusion and/or new injection) should be discontinued, continued after protocol modifications or resumed according to the protocol.

In case of study discontinuation, the Competent Authorities (CA) and Ethics Committees (EC) will be informed and all participants still in follow-up will be contacted for attending an Early Termination visit (see section 7.2.13).

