The fifth and sixth participants of the “Sentinel Groups” will be enrolled the same day, with an interval of at least 3 hours, in cohort B and will receive the high dose vaccine on day 0. Twenty-four hours after the injection, they will be called to collect safety information related to the vaccination.

Following the 14 day follow up of all sentinel subjects, the DSMB will review safety data after the first dose in these six participants, before giving a positive written recommendation for continuing with the double-blind, randomized treatment phase.

| | |
|--|---|
| | 
Following the 42 day follow-up of all sentinel subject, a medical monitoring of safety data will be performed to evaluate safety of the second injection in these six participants. In case of any safety concern, an ad hoc DSMB meeting will be organized before giving a positive recommendation for continuing with the second injection of the double-blind, randomized cohorts (“main cohorts”).
 
In case of any related severe AE or related SAE, Sponsor will be contacted and after the case has been discussed by the Sponsor and DSMB, it will be determined if study vaccination can be continued according to the protocol. Assays will include sero-neutralization, ELISA against SARS-CoV-2 antigens and measles antibodies, Intracellular Staining (ICS) to assess T cell responses and shedding assays (only for sentinel subjects).
 |
| 
7. Primary Objective
 | 
To assess the safety and tolerability of the COVID-19 vaccine following one or two consecutive intramuscular injections in healthy volunteers.
 |
| 
8. Secondary Objectives
 | 
To assess induction of SARS-CoV-2 spike protein-binding antibodies upon one or two administrations of the COVID-19 vaccine by means of ELISA up to study day 91.
 
To assess induction of SARS-CoV-2 neutralizing antibodies upon one or two administrations of the COVID-19 vaccine by means of serum neutralization assay up to study day 91.
 
To assess SARS-CoV-2 spike protein-specific, cell-mediated immune responses up to study day 91 induced by one or two doses of vaccine, by means of intracellular staining and flow cytometry.
 
To assess potential measles virus shedding by means of RT-qPCR of saliva, nasal swab, urine, or blood samples in sentinel groups on day 0, 7, 14, 28 and 42
 |

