| 
18. Study halting rules
 | 
The criteria for considering a contraindication or preventive action to the start of the treatment of the 2nd or 3rd cohort (increasing dosage) or administration of the COVID-19 vaccine to subsequent subjects in the current cohort will be:
 
 - A serious adverse reaction (i.e. a serious adverse event considered at least possibly related to the study vaccine) in one subject. - The occurrence of clinically significant severe (grade 3 or higher) non-serious adverse events considered as at least possibly related to the vaccine administration in two subjects in the same cohort, independent of within or not within the same system-organ-class. Both clinical and laboratory abnormalities are considered. - Any onset of AESI assessed as related to the vaccine by the investigator or by the sponsor. |
| 
19. Main personal data to be collected
 | 
 - Age, sex - Physical examination, with height, weight - Personal medical history & vaccination history - Treatment history - Allergies |

| | |
|---|--|
| | 
 - Pregnancy test results for women - Contraception methods - Safety Laboratory results (see Appendix 1) - ECG |
| 
20. Data collection, transfer, record and management
 | 
The trial data management plan will be issued before data collection begins and will describe all functions, processes, and specifications for data collection, cleaning and validation.
 
The data management documents will describe captured methods, who is authorized to enter the data, decisions about ownership of data, source data storage, which data will be transferred (including timing of transfers), the origin and destination of the data and who will have access to the data at all times.
 |

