| | 
Le DSMB (à l'exception des membres observateurs du DSMB qui n'auront accès qu'au rapport de sécurité en insu) recevra également des rapports et les analyses intermédiaires prévues au protocole :
 
 1. Rapport intermédiaire 1 (RI1) : Lorsque les 6 sujets sentinelles auront effectué la visite 4 du jour 28, 2. Rapport intermédiaire 2 (RI2) : lorsque les 6 sujets sentinelles auront effectués la visite 5 du jour 42 comme indiqué ci-dessus 3. Rapport intermédiaire 3 (RI3) : Lorsque tous les sujets (ou au moins 50 % en fonction du taux de recrutement) auront effectué la visite 4 du jour 28. 
Une dernière réunion du DSMB sera organisée après que tous les sujets auront terminé la visite 8 (jour 210) pour être informé des résultats globaux de l'étude. Après la décision du promoteur, des réunions ad hoc du DSMB pourraient être prévues pendant toute la durée de l'étude.
 
Une charte du DSMB sera rédigée. Les recommandations du DSMB seront également transmises aux Autorités compétentes, au représentant du développeur du vaccin, et à l'IRB Institut Pasteur.
 |
| 18. Règles d'arrêt de l'étude | 
Les critères pour envisager une contre-indication ou une action préventive au démarrage du traitement dans la 2^e ou la 3^e cohorte (montée de dosage) ou à l'administration du vaccin contre la COVID-19 aux sujets suivants dans la même cohorte seront :
 
 - Une réaction indésirable grave (c.-à-d. un événement indésirable grave considéré comme au moins possiblement lié au vaccin à l'étude) chez un sujet. - La survenue d'événements indésirables non graves sévères (grade 3 ou plus) cliniquement significatifs, considérés comme possiblement liés à l'administration du vaccin chez deux sujets de la même cohorte, que ces EI concernent ou non la même classe de systèmes d'organes. Les anomalies cliniques et biologiques sont prises en compte. - Toute apparition d'événement indésirable d'intérêt particulier (EIIP) évalué comme lié au vaccin par l'investigateur ou par le promoteur. |
| 19. Principales données à caractère personnel recueillies | 
 - Âge, sexe - Examen physique, avec taille et poids - Antécédents médicaux personnels et antécédents de vaccination - Antécédents de traitement - Allergies - Résultats du test de grossesse pour les femmes - Méthodes de contraception - Résultats des analyses biologiques de sécurité (voir l'annexe 1) - ECG |

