- The fifth and sixth participants of the “Sentinel Groups” will be enrolled, the same day with an interval of at least 3 hours, in cohort B and will receive the high dose vaccine on day 0. 24 hours after the injection, they will be called to collect safety information related to the vaccination.
- Following the 14 day follow up of all sentinel subjects, the DSMB will review safety data after the first dose in these six participants, before giving a positive written recommendation for continuing with the double-blind, randomized treatment phase.

Following the 42-day follow-up of all sentinel subject, a medical monitoring of safety data will be performed to evaluate safety of the second injection in these six participants. In case of any safety concern, an ad hoc DSMB meeting will be organized before giving a positive recommendation for continuing with the second injection of the double-blind, randomized cohorts (“main cohorts”). In case of any related severe AE or related SAE, Sponsor will be contacted and after the case has been discussed by the Sponsor and DSMB it will be determined if study vaccine can be continued according to the protocol.

All subjects included in the “Sentinel Groups” will be included in the shedding assessment. Body fluids including saliva, nasal swab, urine and whole blood will be collected therefore at visit 1 (day 0), visit 2 (day 7), visit 3 (day 14), visit 4 (day 28) and visit 5 (day 42).

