- an identifiable reporting source (investigator contact details).

In all cases, all SUSAR, relevant complementary information should be collected and notified within 8 extra-days:

- From the first report for deaths and life-threatening event,
- From the end of the allowed delay set for other SUSAR and event of medical importance.

Expedited reporting to CAs, ECs and investigators of each site will be managed by SGS Medical Affairs according to the SOP “Processing and Reporting of Individual Serious Adverse Events of Interventional Clinical Trials”, the ICH guideline E2A “Note for Clinical Safety Data Management” and the Safety Management Plan. CRAs will be in charge to inform investigator of each site. Acknowledgment of Receipt will be completed and signed by the investigator and then retrieved by the CRA.

In addition to this expedite reporting to Competent Authorities and Ethics committees, the overall SAE/SUSAR notified by investigator will be reported to Competent Authorities and Ethics Committees via the Annual report of Safety (see section 9.1.12.7).

If a SUSAR or IMP are likely to endanger the immediate safety of the study participant, the sponsor and the investigator should put in place urgent safety measures to protect the participants.

If urgent safety measures are put in place, Competent Authorities and Ethics Committees should be immediately informed and a protocol amendment should be submitted to the CA/EC within 15 days.

Participant will be informed about the new safety measures by the investigators as soon as possible (e.g. prior next dosing as appropriate) and through an updated informed consent.

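### Section 4.9.1 names three study halting criteria but leaves the pause before DSMB review optional, and no other section states that dosing stops meanwhile

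*Protocol*

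**What the plan says.** Section 4.9.1 of the protocol begins "The study could be temporally suspended, pending a full DSMB safety review". It then introduces three triggers with the words "The criteria for considering a contraindication or preventive action":

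1. one serious reaction at least possibly related to the vaccine;
2. clinically significant, related non-serious events of grade 3 or higher in two subjects of one cohort;
3. "Any onset of AESI assessed as related to the vaccine by the investigator or by the sponsor".

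Once the DSMB has completed its review, the sponsor decides whether inclusions and injections "should be discontinued, continued after protocol modifications or resumed according to the protocol".

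Synopsis item 18 repeats the triggers with the same introduction but does not mention suspension. The French synopsis matches it: "Les critères pour envisager une contre-indication ou une action préventive".

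Synopsis item 6 and section 3.2 add a separate step: "In case of any related severe AE or related SAE, Sponsor will be contacted". In section 3.2, once sponsor and DSMB have discussed the case, "it will be determined if study vaccine can be continued according to the protocol". Section 1.4 presents halting rules, for individuals and for treatment, as part of the trial's safety monitoring.

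**The concern.** A study halting rule protects the remaining volunteers in the interval between a triggering event and the decision that follows review. In section 4.9.1 the action is permissive twice over: the study *could* be suspended, and the criteria are for *considering* action. Yet the same section speaks of suspension *pending* review and of the study being *resumed*, which makes sense only if dosing has stopped. The intention and the instruction do not match.

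This is a first-in-human trial of a live vectored vaccine in healthy adults at two sites. If a criterion is met during the randomized phase, the protocol should tell both sites whether the next scheduled injection goes ahead. As written, it does not.

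**Working it through.** The plan attaches no figure to its halting rules, so the main check is textual.

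**Step 1. Is a hold stated or implied for each criterion?**

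| Criterion in 4.9.1 | Other text that bears on it | Does it state that dosing stops? |
|---|---|---|
| 1. One related serious reaction | Item 6 and section 3.2: continuation decided after sponsor and DSMB discussion | Implied, not stated |
| 2. Related grade 3+ events, two subjects in a cohort | Same text, which applies from the first related severe AE | Implied, not stated |
| 3. Related AESI that is serious or severe | Same text | Implied, not stated |
| 3. Related AESI that is neither | None | Neither stated nor implied |

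The last row is not empty in practice. Section 9.1.12.2 lists anosmia and dysgeusia among the AESIs. It also says that AESIs may be non-serious and may be early signs of something worse.

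**Step 2. Do other provisions supply the hold?**

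- Section 9.1.12.3 requires urgent safety measures, but on a narrower condition: "If a SUSAR or IMP are likely to endanger the immediate safety of the study participant".
- Section 4.12 allows unscheduled DSMB meetings at the request of the sponsor or the DSMB. They are possible, not required, and the section does not say what happens to dosing before they take place.
- Section 4.8 discontinues an affected individual from further vaccination. It does not protect the others.
- Gates exist at each sentinel step, before randomization, and at the sentinel Day 42 review that precedes the main cohorts' second injection. They act at fixed points, not on an event arising later in the randomized phase.

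The gap therefore concerns mainly the 84 randomized participants (section 3.3).

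**Step 3. Illustration of pace.**

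Inputs are 84 main-cohort participants, with 21, 21 and 24 on active vaccine at Day 0 (Table 1), cohort C on placebo at Day 28 (Table 1), and a provisional inclusion period of about 6 weeks (synopsis item 23). Two assumptions are needed: that the 6 weeks (42 days) apply to the main cohorts, and that accrual is even.

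- First injections: 84 / 42 = 2.0 a day. Active share (21 + 21 + 24) / 84 = 66 / 84 = 78.6%, so 2.0 × 0.786 = 1.6 active a day.
- Second injections, once due: also about 2.0 a day. Active share (21 + 21) / 84 = 42 / 84 = 50%, so 1.0 active a day.
- Over an assumed 7-day review: 7 × 2.0 = 14 first injections, of which 14 × 0.786 = 11 active; or 14 second injections, of which 7 active.
- Over an assumed 3 to 14 days: 6 to 28 first injections, of which about 5 to 22 active.

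No review time is given in the protocol, so the 7 days and the 3-to-14-day range are chosen only to show scale.

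**The case against.** The strongest reply is that section 4.9.1 should be read as a whole and together with item 6 and section 3.2. Under its heading and its references to pending review and resumption, a pause is plainly meant, and the fault comes down to one modal verb. For related severe AEs and related SAEs, continuation already depends on a discussion with the DSMB, and from a single related severe AE rather than two. Item 6 does not limit this to sentinels. Most listed AESIs, such as acute respiratory distress syndrome or meningitis, would ordinarily be serious or severe and so fall under it. The DSMB charter and the Safety Management Plan, which are not shown, may set the operational hold.

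Much of this stands. A reader might infer that the protocol lets the sponsor dose freely through any serious reaction, or that section 1.4 claims a safeguard that does not exist. The documents support neither: criteria are defined, and continuation after the graver events is conditional on discussion. What the reply does not supply is a sentence saying that injections stop while that discussion takes place. Both sites work from the protocol, and the instruction belongs there.

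A second reply is that discretion is sensible before closing two sites for one mild taste disturbance, possibly in a placebo recipient. That is a fair view of how wide criterion 3 should be. But the criterion already requires the event to be judged vaccine-related, and if it is thought too wide, narrowing it is better than leaving all three criteria optional.

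Third, a trial-wide hold is not the same as the individual delay for fever or acute disease allowed in section 7.2.6. It could push many second injections outside their window and thin the per-protocol population used for the titre comparison in section 12.4. This is correct, and the fix has to deal with it.

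**Conclusion.** The point holds in a limited form. Suspension pending DSMB review is permissive where the section's own words intend a pause. The hold is implied but not stated for related severe AEs and related SAEs, and it is absent for a related AESI that is neither serious nor severe. The wording should be corrected because the protection is cheap and the participants are healthy volunteers in a first-in-human trial.

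The size cannot be fixed from the document. A reader might take the pace of about 2 injections a day as an estimate of the volunteers put at risk. It is not: it rests on even accrual over a provisional 6 weeks, on a review time the protocol does not give, and on the sponsor choosing not to pause. The conclusion rests on the text alone and affects no stated statistical quantity. A stricter DSMB charter would reduce the practical risk but would not remove the ambiguity in the protocol.

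**What to change.** Replace the first sentence of section 4.9.1 with: *If any criterion below is met, new inclusions and further injections will be temporarily suspended at both sites until the DSMB has reviewed the data and the sponsor has decided.* Align synopsis item 18 in English and French.

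Add to section 12.1 that a second injection given late only because of such a hold is not a major deviation for the per-protocol population. That population requires two injections according to protocol, so without this addition the hold could remove participants from it.

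The cost is a few sentences of text and, when a criterion is met, a short stop in recruitment and dosing, with some second injections outside Day 28±3. Those participants would have a longer dosing interval, which should be reported alongside the immunogenicity results.

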3.3. Blinded / randomized cohorts

After DSMB review and positive recommendation, sponsor will decide to continue the study by the enrollment of the remaining 84 participants (“Main Cohorts”), in a blinded randomized manner, in the low dose group (cohort A) or in high dose groups (cohort B and C).

Table 1: Treatment groups allocation

| Cohort | Treatment | Injection 1 D0 | Injection 2 D28 | Number of participants | | |
|--------|----------------------|-------------------|--------------------|------------------------------|------------------------------|---------|
| | | | | COVID-19 vaccine Sentinel | COVID-19 vaccine Main grp | Placebo |
| A | COVID-19 low Dosage | Vaccine | Vaccine | 3 | 21 | 6 |
| B | COVID-19 high Dosage | Vaccine | Vaccine | 3 | 21 | 6 |
| C | COVID-19 high Dosage | Vaccine | Placebo | 0 | 24 | 6 |

Participants will be observed closely for safety and immunogenicity from the first injection to the end of study.

The investigator, and site personnel performing study related assessments, all participants, as well as the sponsor’s representatives involved in the monitoring and conduct of the study will be blinded.

Only site personnel performing randomization, preparation of IMP and monitoring of the IMP handling process will be unblinded as well as the DSMB members (excluding observing DSMB members who will only have access to blinded safety report).

During the follow up phase (after all subjects have completed V6), the head of vaccine programs of Institut Pasteur and a project manager from the vaccine developer (Themis Bioscience GmbH a subsidiary of Merck & Co., Inc., Kenilworth, New Jersey USA,) will have access to the unblinded data for the purpose of immunogenicity assessment. In the current pandemic, rapid assessment of the potential of the vaccine, including the balance of safety and immunogenicity is required to move promising candidates forward as quickly as possible. All data will be stored on a secured server accessible with a login and password to which only the unblinded person has access. The risk of impact on the study is minimized as unblinding will occur when the treatment phase will have been completed, the analyses have been defined, and the unblinded personnel is not involved in the clinical evaluation and management of the participants.

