4.11. Allocation of Subjects to Treatment groups

➤ **Unblinded/non randomized – “Sentinel Groups”**

The 6 first participants enrolled in the study will be treated sequentially in an unblinded and non-randomized manner. Three from cohort A and three from cohort B will received the low and high dose, respectively.

➤ **Blinded/randomized - Cohort A (low dose or placebo, two injections)**

21 subjects treated with low dose on days 0 + 28 and 6 subjects treated with placebo on days 0 + 28.

➤ **Blinded/randomized - Cohort B (high dose or placebo, two injections)**

21 subjects treated with high dose on days 0 + 28 and 6 subjects treated with placebo on days 0 + 28.

➤ **Blinded/randomized - Cohort C (high dose or placebo, two injections)**

24 subjects treated with high dose on day 0 and with placebo on day 28 and 6 subjects treated with placebo on days 0 + 28.

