4.11.1. Randomization procedures

A total of 84 participants will each be randomly assigned to one of three different cohorts, receiving either one or two COVID-19 vaccinations or one or two placebo injections at the allocation ratio 7: 2 for cohort A and B and 4: 1 for cohort C.

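### The halting count for related non-serious grade 3+ events is kept per cohort, although cohorts B and C have had the same single high dose until injection 2

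*Protocol*

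**What the plan says.** Section 4.9.1 lists three criteria that may lead to suspension pending a DSMB safety review. Two are not tied to a cohort: a single serious adverse reaction, and any AESI judged related. The third, for clinically significant non-serious events of grade 3 or higher, needs events "considered as at least possibly related to the vaccine administration in two subjects in the same cohort".

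The rule is written for a stepwise escalation. It governs the "start of the treatment of cohort B and C (increasing dosage") and further dosing in whichever cohort is under way. Synopsis item 18 speaks likewise of the "start of the treatment of the 2nd or 3rd cohort (increasing dosage"). After the DSMB review, the "sponsor will decide if the study (i.e. new inclusion and/or new injection) should be discontinued", modified or resumed.

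Only the six sentinels are dosed stepwise. Section 3.3 then enrols the rest "in a blinded randomized manner, in the low dose group (cohort A) or in high dose groups (cohort B and C"), and Section 4.11.1 says "A total of 84 participants will each be randomly assigned to one of three different cohorts". Under Section 4.11, cohort B has "21 subjects treated with high dose on days 0 + 28"; cohort C has 24 who receive the high dose on day 0 and placebo on day 28. Each cohort also has 6 placebo recipients.

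No section gives a count by dose level, or one pooled over B and C, for the third criterion.

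**The concern.** Between injection 1 and injection 2, the labels B and C record what a vaccinee will receive on day 28, not what he or she has received so far. A related grade 3 reaction in one B vaccinee and another in one C vaccinee are two reactions to the same high dose. Read literally, they do not meet the criterion, whereas two in B alone or two in C alone do.

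The timing gives this its weight. The trial is first-in-human, the exposure concerned is the higher dose, and the count matters most while first high doses are still being given and before cohort B receives its second. The scheduled reports do not fill the interval. Intermediate Reports 1 and 2 follow the sentinels' visits. Intermediate Report 3 waits until all, or at least half, of the subjects have completed visit 4, which is the visit of the second injection.

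**Working it through.** **Plan's own figures.** The cohort sizes reproduce: (21+6) + (21+6) + (24+6) = 84, and 84 + 6 sentinels = 90. The ratios 21:6 = 7:2 and 24:6 = 4:1 agree with Section 4.11.1. The protocol gives no operating characteristics for the halting rule and no expected rate of related grade 3+ events.

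**Inputs.** Main-phase high-dose recipients at injection 1: 21 in B and 24 in C, 45 in all (Section 4.11). Threshold: two subjects (Section 4.9.1). Assumed: a common rate *p* of related non-serious grade 3+ events per vaccine injection, independent subjects, and no such events after placebo.

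**Split pairs.** If exactly two of the 45 have an event and all are at equal risk, the chance that one is in B and one in C is 21 × 24 / C(45,2) = 504/990 = 50.9%. No value of *p* is needed.

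**Main phase, after injection 1.**
- As written: 1 − P(X₂₁ ≤ 1) × P(X₂₄ ≤ 1).
- Pooled: P(X₄₅ ≥ 2).
- The gap is the probability of exactly one event in each cohort: 21p(1−p)²⁰ × 24p(1−p)²³ = 504p²(1−p)⁴³.

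At *p* = 2%: as written, 1 − 0.935 × 0.917 = 14.3%; pooled, 1 − 0.403 − 0.370 = 22.7%. At *p* = 5%: as written, 1 − 0.717 × 0.661 = 52.6%; pooled, 1 − 0.099 − 0.236 = 66.5%.

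| Assumed rate | As written | B and C pooled |
|---|---|---|
| 1% | 4.2% | 7.5% |
| 2% | 14.3% | 22.7% |
| 3% | 27.0% | 39.3% |
| 5% | 52.6% | 66.5% |
| 10% | 89.3% | 94.8% |
| 15% | 98.4% | 99.4% |

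The gap is largest at p = 2/45 = 4.4%, where it is 14.1 points.

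**About half enrolled (11 in B, 12 in C).** At 5%: 20.8% as written, 32.1% pooled. At 10%: 54.0% and 68.5%.

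**Whole trial, sentinels included (24 vaccinees per cohort, both injections).** Let q = 1 − (1−p)² be the chance of an event after either of two vaccine injections.
- Cohort A meets the criterion with probability 1 − P(X₂₄,q ≤ 1): 24.6% at 2%. The added count does not change this.
- B and C as written: 1 − P(X₂₄,q ≤ 1) × P(X₂₄,p ≤ 1), which is 30.8% at 2%.
- B and C with the added count: 1 − {(b₀+b₂)(c₀+c₁) + b₁c₀}, with b₀ = (1−q)²⁴, b₁ = 24p(1−q)²³, b₂ = 24p(1−p)(1−q)²³, c₀ = (1−p)²⁴ and c₁ = 24p(1−p)²³. This is 36.5% at 2%.
- Whole trial at 2%: 1 − 0.7544 × 0.6921 = 47.8% as written; 1 − 0.7544 × 0.6349 = 52.1% with the added count.
- At 1%: 17.7% and 20.4%. At 5%: 93.8% and 95.1%. The largest gap is 4.3 points, near 2.1%.

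**The case against.** The best answer is that a stricter trigger may already exist. Synopsis item 6 has any related severe AE discussed by the sponsor and the DSMB, who determine whether vaccination continues. That is a threshold of one event, it names no sentinel limit, and it follows a sentence about the main cohorts. If it applies throughout, every B/C pair would have been escalated at its first event. Against that, the body of the protocol repeats the sentence only in Section 3.2, which is about the sentinels. Its reach into the main phase is arguable but not stated.

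Other routes also stand. Section 4.8 stops further vaccination of a subject with one such event and has the sponsor notified immediately. Section 4.12 allows an unscheduled meeting at the request of the sponsor or the DSMB, and Section 3.3 says that site staff who randomise and prepare the product "will be unblinded as well as the DSMB members" (observers excepted). The DSMB could therefore see that both events followed the same dose. These routes soften the consequence, but Section 4.8 counts nothing across subjects and an unscheduled meeting is discretionary. The DSMB charter, not shown, might add a pooled count; it would still differ from the rule in the protocol.

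It can also be said that cohorts are the planned regimens, so counting by cohort is coherent. That holds after injection 2, when B and C differ. It does not hold before.

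**Conclusion.** The point stands, with minor to moderate importance. The third criterion is fixed in sequential-cohort wording that does not fit the concurrent main phase, and it divides one exposure group of 45 into 21 and 24. About half of all two-event patterns after the first high dose miss it. Under assumed rates, pooling raises the main-phase chance of meeting it after injection 1 by at most about 14 points; the whole-trial rise is at most 4.3. The gain is therefore mainly an earlier and more certain review. The percentages rest on assumed rates, independence, equal risk in B and C, and no placebo events judged related; they give no credit to the other routes.

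Three stronger readings are not supported:
- A reader might infer that two high-dose reactions would go unreviewed. The individual stopping rule, sponsor notification and ad hoc DSMB meetings make that too strong.
- A reader might infer that a pooled count would have halted the trial. Section 4.9.1 says only that the study could be suspended, so the figures are chances of prompting a review.
- A reader might count all 48 first high-dose recipients, giving 24 × 24 / C(48,2) = 576/1128 pairs. That includes 3 × 24 = 72 pairs of a B sentinel with a C vaccinee, although the DSMB reviews the sentinels' day 0 to 14 data before any cohort C dosing. The main-phase figure is the right one, and the share is still 51%.

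Serious reactions, related AESIs, cohort A and events after injection 2 are not affected.

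**What to change.** In Section 4.9.1 and synopsis item 18, keep the within-cohort count and add: *or in two subjects at the same dose level with onset after injection 1 and before injection 2 (cohorts B and C pooled)*, counted by the unblinded DSMB members. Mirror this in the DSMB charter.

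The cost is one clause, matching charter text and a running count by dose received. DSMB reviews become slightly more frequent, within the gaps given above. No existing trigger is lost and no further unblinding is needed. The cohort count should not be replaced by a count per injection: that would drop same-cohort pairs split across injections, and at 5% per injection cohort A's chance of meeting the criterion would fall from 69% to 56%.

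Separately, the sponsor should state whether the single-event escalation in synopsis item 6 and Section 3.2 covers the main phase. Extending it to everyone is the sponsor's choice, with a larger review burden. There are 42 + 42 + 24 = 108 planned main-phase vaccine injections, so at an assumed 2% the chance of at least one such event is 1 − 0.98¹⁰⁸ = 88.7%. The added count does not depend on that choice.
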